proprietary, biocompatible hydrogel particles synthesized with starting materials that are Generally Recognized as Safe by the U.S. Food and Drug Administration (FDA).¹⁰ CSP01 is similar to Gelesis100 and Gelesis200, both of which have been tested in humans and show excellent safety profiles, and differs from Gelesis200 only by the addition of the excipient sodium stearyl fumarate, which allows for the packing of more hydrogel particles into the capsule. CSP01 capsules are taken prior to a meal with water, after which the small particles within the capsules hydrate and expand in the stomach and small intestine. Gelesis100, a similar product, has undergone multiple early phase clinical trials.¹¹ The First Loss Of Weight (FLOW) study demonstrated the safety of the Gelesis100 medical device with 12 weeks of use in overweight and obese subjects. Currently, Gelesis Inc. is conducting the Gelesis Loss Of Weight (GLOW) study, a pivotal, randomized, double-blind, placebo-controlled, parallel-group study designed to assess the effect of repeated administration of Gelesis100 over six months on body weight and glycemic control parameters in overweight and obese subjects.¹²

c.) Rationale behind the proposed research

By acting as a bulking agent and possibly reducing colonic transit time through increase of colonic water content, CSP01 may contribute to constipation relief. In contrast to traditional fiber that retains water without influencing colonic water content, CSP01 absorbs water solutions up to 85 times its original weight while in the stomach, acts as a bulking agent as it moves through the small intestine, and partially degrades in the large intestine through loss of its three-dimensional matrix structure and most of its hydration capacity. By losing its water absorption capacity in the colon, colonic water content is thus increased in a mechanism of action similar to current therapies treating constipation, and CSP01 is expelled in the feces.

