If there is an issue with capsule transit, will be monitored by investigator team and depending on location may exclude patient (i.e. if capsule transit delayed in stomach, would exclude patient based on exclusion criteria of gastroparesis). Patients with no bowel movement for 5 consecutive days, who are in need of a rescue treatment, will be instructed to contact the investigator. The following treatment is recommended, as applicable, in the following order:

- 1. Glycerin suppository
- 2. Enema
- 3. Laxadin/Bisacodyl tablets (3x5mg)

Administration of rescue treatment is at the discretion of the investigator based on an assessment of the subject; administration of rescue should be monitored and recorded.

3. Treatment Period (Day 0 to 22)

- a. **Day 0:** On the visit to initiate treatment, patients will return to the clinic to return their WMC monitor and be treated in a parallel-group design for 3 weeks. At this visit, the patient will return the SmartPill receiver and the study diary. Questions or concerns about the study will be discussed, including any changes in concomitant medications and new or worsening adverse events. If available, results of the SmartPill test will be reviewed by the patient's physician. If it is unclear that the capsule has passed, based on the subject's history or on the study results, erythromycin may be prescribed if the capsule is still in the stomach as a promotility medication or obtain an abdominal x-ray for verification to determine if the capsule is still in the colon. If the subject is female, then a urine pregnancy test will be performed before any abdominal xray. Issues with capsule transit will be addressed as above.

- b. Following the two-week run-in period, subjects will again complete the Rome IV Constipation module confirming that inclusion and exclusion criteria continue to be satisfied, and the patient will be randomized using the IWRS. The IWRS will notify the pharmacy to prepare the study drug (randomization output must only be seen by unblinded pharmacist).
- c. During 3-week treatment period, patients will ingest three capsules, twice daily, before breakfast and dinner (with 16 oz water).
- d. Patients will be asked to refrain from making any major lifestyle changes (e.g., starting a new diet or changing their exercise pattern) during the study.

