 - iii. Probably not related: temporal association is such that the medical device use is not likely to have had any reasonable association with the observed event.
 - iv. Not related: no relationship to the use of the medical device is perceived.
- f. Abnormalities of vital signs and laboratory results are to be recorded as AEs only if they are considered by the Investigator as clinically significant (symptomatic, requiring corrective treatment, leading to discontinuation, or fulfilling a seriousness criteria).
- g. Any pre-existing conditions or signs and/or symptoms present in a subject prior to the Screening Visit should be recorded as medical/surgical history.
- h. In this study, the following events will be reported to the authorities on expedited basis:
 - i. All SAEs (including SADEs) will be expeditiously reported to the relevant European Regulatory Authorities and the Ethics Committees.
 - ii. All suspected USADEs will be expeditiously reported to the Food and Drug Administration (FDA) and Institutional Review Board.
- i. All device deficiencies are to be recorded in the appropriate electronic CRF.

6. Anticipated Adverse Device Effects

- a. The ADEs anticipated with the administration of Gelesis100 in overweight or obese subjects include nausea, dyspepsia (heartburn), abdominal distension (bloating), flatulence, abdominal pain, diarrhea, defecation urgency, and constipation. These AEs were observed in the FLOW study. A comprehensive list of anticipated ADEs is provided in the Investigator's Brochure (8).\

7. Risk Analysis

- a. The Sponsor has established and maintains a process for identifying hazards associated with the use of its products, estimating, evaluating, controlling these risks and monitoring the effectiveness of the control. Detailed information regarding risk analysis is available in the Investigator's Brochure (8).

8. Precautions to Minimize Risk

- a. To minimize technical and medical complications, the investigational medical device should be used only as instructed in the Clinical Investigation Plan. This includes:
 - i. administering the prescribed amount of medical device before breakfast and dinner (3 capsules at each)

- ii. drinking the prescribed volume of water (approximately 100 mL + 500 mL) at the prescribed timing before meal
- iii. consuming food at the prescribed timing (20 to 30 min after medical device administration)

9. Pregnancy

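### The water volume for each dose is 16 oz in the treatment section but about 600 mL in the precautions that are meant to minimize complications; the two must be reconciled

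*Combined protocol and SAP*

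**What the plan says.** Section V.a.3.c (Treatment Period) gives the dosing instruction: "patients will ingest three capsules, twice daily, before breakfast and dinner (with 16 oz water"). It does not divide the water into portions and gives no interval before food.

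Section V has two subsections lettered c. The second, Adverse events, contains item 8, Precautions to Minimize Risk. It opens: "To minimize technical and medical complications, the investigational medical device should be used only as instructed in the Clinical Investigation Plan". It then lists three parts of correct use:

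- the dose: "administering the prescribed amount of medical device before breakfast and dinner (3 capsules at each")
- the water: "drinking the prescribed volume of water (approximately 100 mL + 500 mL) at the prescribed timing before meal"
- the food: "consuming food at the prescribed timing (20 to 30 min after medical device administration")

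Section I.b describes how the product works (its sentence goes on to name the small bowel as well): "CSP01 capsules are taken prior to a meal with water, after which the small particles within the capsules hydrate and expand in the stomach and". It names no volume. Nothing else in the protocol explains the 100 mL and 500 mL portions or relates them to 16 oz.

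**The concern.** Both instructions are current operative text, and both cover the same occasion: three capsules before breakfast and three before dinner. Item 8 speaks of a prescribed volume, but the only other place that prescribes one gives a different total.

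Two things are at stake. First, the protocol itself makes the water volume a safety precaution, so a site working from the treatment section would depart from it without knowing. Second, Adverse events item 3 counts errors in using the device, and inadequate labels, as device deficiencies. Item 5.i requires all deficiencies to be recorded, and item 3.a treats some of them as serious adverse events. With two volumes on paper, a use error in water intake has no single reference.

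**Working it through.** The plan states no derived figure here, so there is nothing to reproduce. The check is a unit conversion.

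**Inputs from the protocol**
- Treatment section (V.a.3.c): 16 oz per dose, two doses a day.
- Precautions (Section V, Adverse events, item 8.a.ii): 100 mL + 500 mL = 600 mL, qualified as approximate.

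**Assumption.** The protocol does not say which ounce it means. Three conventions are shown; the conversion factors are standard and do not come from the documents.

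**Formulas.** V = 16 × (mL per oz). Gap = 600 − V. Excess of 600 mL over 16 oz = 600/V − 1. Shortfall of 16 oz against 600 mL = 1 − V/600.

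| Ounce | mL per oz | V (mL) | Gap (mL) | Excess | Shortfall |
|---|---|---|---|---|---|
| US fluid | 29.5735 | 473.2 | 126.8 | 26.8% | 21.1% |
| US label | 30.0 | 480.0 | 120.0 | 25.0% | 20.0% |
| Imperial | 28.4131 | 454.6 | 145.4 | 32.0% | 24.2% |

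At two doses a day the gap is 2 × 126.8 = 253.6 mL (240.0 to 290.8 mL across conventions). No convention brings 16 oz to 600 mL.

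**Does 16 oz stand for the 500 mL portion alone?** The remaining differences are 500 − 480.0 = 20.0 mL, 500 − 473.2 = 26.8 mL and 500 − 454.6 = 45.4 mL, so 16 oz is 4.0%, 5.4% or 9.1% below 500 mL. That is close enough to be rounding. The other 100 mL is still missing from V.a.3.c, and the totals still differ by 120 to 145 mL.

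**Is the 600 mL a daily amount?** Item 8 does not say per dose in so many words. Its neighbouring entries describe a single dosing occasion, which supports the per-dose reading. If 600 mL were the daily total, V.a.3.c would give 2 × 473.2 = 946.4 mL a day, and the two would differ by more, in the other direction. Neither reading reconciles them.

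**The case against.** The best defence is that V.a.3.c gives the main drink, rounded, and leaves out the smaller portion. Item 8 does say that its volumes are approximate. This narrows the conflict to an omitted 100 mL plus rounding, but the protocol does not say so, and a qualifier of approximation does not stretch to a shortfall of 20 to 24%.

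Four other limits stand in full, and each rules out something that a reader might infer.

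- **That the meal timing also conflicts.** It does not. The 20 to 30 minute interval and the division of the water appear only in item 8, and both fit with dosing before breakfast and dinner in V.a.3.c. Only the total volume is contradicted.
- **That patients actually drank different amounts, so that exposure and tolerability varied.** This is a single-center study, and the patient instruction sheet is not among the documents. All patients may be told one volume.
- **That there is no standard for correct use at all.** Capsule number, frequency and food timing are each stated consistently or only once. The gap concerns water volume alone. The per-protocol definition in Section VI does not use water volume, so no analysis population depends on it.
- **That 16 oz is too little for the product to hydrate.** Sections I.c and V.b.1 give uptake of up to 85 times its weight and 2.37 g per dose: 85 × 2.37 = 201 g. Both volumes exceed that. This does not show that either is right; it shows only that the documents do not support a claim of insufficient water.

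**Conclusion.** The concern holds as an internal inconsistency in a safety-related instruction. The two totals for the same dose differ by about 127 mL (120 to 145 mL), so that the volume in the precautions is 25 to 32% larger than the volume in the treatment section.

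This rests on two assumptions: that item 8 refers to each dose, as its neighbouring entries suggest, and that the Clinical Investigation Plan named there is this protocol.

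A reader might go further and infer a biased treatment comparison. The documents do not support that: V.a.3.c makes no distinction between arms, and patients and study staff other than the pharmacist are blinded. Power and sample size do not use the water volume. Whether the difference changes tolerability or colonic transit cannot be derived from the documents. The point deserves correction because the protocol presents the volume as a precaution, not because it threatens the trial's conclusions.

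**What to change.** Reconcile V.a.3.c and Adverse events item 8.a.ii to a single total water volume per dose. State in V.a.3.c how that volume is divided, if it is. Carry the meal interval already given in item 8 across to V.a.3.c, or cross-refer to it. Make the patient instructions match. Which volume is right is for the sponsor and the investigator to decide.

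The cost is wording in two places of the protocol and a check of the instruction sheet, submitted to the IRB as an amendment. No change to the design, sample size or analysis is needed.

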- e. Patients will be instructed to complete a simple, web-based daily diary using the Redcap system throughout the duration of the study which includes daily recording of number and time of bowel movements, complete/incomplete evacuation, and straining, abdominal discomfort, bloating, constipation severity, and overall relief using a nominal rating scale.
- f. **Day 1:** Subjects will begin taking study device. Patients will complete the Patient Assessment of Constipation Symptoms (PAC-SYM) and Quality of Life (PAC-QOL) to determine the severity of their constipation.
- g. **Day 15:** Following 14 days of treatment, patients will return to the clinic to undergo WMC testing to establish their motility profile on treatment and complete PAC-SYM, PAC-QOL questionnaires.
- h. **Day 22:** Following 21 days of treatment, patients will return to the clinic to return the WMC monitor and complete PAC-SYM, PAC-QOL questionnaires.
- i. **Day 31 (+3 days):** There will be a post-treatment period of 7 days during which time patients will continue to complete their daily diary. The clinical coordinator will call patients at the end of this follow-up period to ensure no adverse events occurred. After completion of the study, patients will be mailed the results of their SmartPill baseline test.

4. Schedule of Events

		Study						
		Run-in period			Treatment period			Post-treatment period
Time Point	Day -28 to -15	Day -14	Day -7	Day 0	Day 1	Day 15	Day 22	Day 31
Eligibility screen	X							
Informed consent	X							
Allocation				X				
CSP01 group				—————				
CMC group				◀	—————			▶
Placebo group				—————				
Rome IV questionnaire	X			X				
Daily diary		X	X	X	X	X	X	X
PAC-SYM		X		X	X	X	X	
PAC-QOL		X		X	X	X	X	
WMC testing			X			X		
Adverse events					X	X	X	X

5. There will be no routine monitoring of labs or imaging for the purposes of the study outside of usual care. Other study monitoring activities will be conducted as per Section IX of this protocol.
6. Patients enrolled in the study will not be allowed to be given standing laxative medications for prophylactic purposes, but rescue medications will be allowed on an as-needed (PRN) basis

b.) Investigational Product (IP) to be used

1. The IP will be supplied by the Sponsor and stored in the MGH inpatient pharmacy
 - a. CSP01 is supplied in capsule form (0.79 g per capsule, 2.37 g per dose)
 - b. CMC dose is supplied in capsule form (0.70 g per capsule, 2.1 g per dose)

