2. Specific data to be collected through patient-reported questionnaires
 - a. Spontaneous Bowel Movement (SBM) frequency rate
 - b. Complete Spontaneous Bowel Movement (CSBM) frequency rate
 - c. Stool consistency (Bristol Stool Form Scale)
 - d. Straining (Ease-of-Passage Scale)
 - e. Abdominal discomfort (Self Assessment on 0–10-point numerical rating scale)
 - f. Bloating (Self Assessment on 0–10-point numerical rating scale)
 - g. Constipation severity (Self Assessment on 0–10-point numerical rating scale)
 - h. Overall relief (Self Assessment on 0–10-point numerical rating scale)
 - i. Balloon Expulsion Time (BET) before and after
 - j. Constipation symptom severity (PAC-SYM)
 - k. Constipation quality of life (PAC-QOL)
 - l. Need for rescue laxatives
3. Study endpoints – As above
4. Statistical methods
 - a. Analysis populations
 - i. Intent-to-treat (ITT) population: all patients who are randomized will be included in the ITT population. This will be the primary population for all analyses of demographics, patient characteristics and disposition, and efficacy data.
 - ii. Safety population: All patients who are randomized and receive any study treatment will be included in the safety population. This will be the primary population for all analyses of safety data
 - iii. Per-Protocol (PP) population: All patients who are randomized and receive the study medication on each day of their hospitalization. Major protocol violations include the following:
 1. Prohibited concomitant medication usage (specifically standing laxatives during hospitalization)The PP population may be used for supplementary analysis of selected efficacy and safety data, as appropriate.
 - b. Endpoint analyses
 - i. Primary endpoint: Colonic transit times will be compared in a paired fashion for individual patients before and after the intervention by means of a repeated measures ANOVA using a 3x2 design to distinguish between the outcomes of the three different groups. We will also use multivariable linear regression to compare change in transit time after adjusting for confounders, specifically: presence of IBS-C, abnormal balloon expulsion testing indicating dyssynergic defecation ($BET \geq 2$ minutes), age, and sex.

ii. Secondary endpoints: The secondary endpoints will be compared in a similar fashion, with logistic regression adjusting for confounders.

c. Power analysis

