 - ii. Documentation that patient meets eligibility criteria, i.e., relevant medical history, physical examination, and confirmation of diagnosis
 - iii. Dated notes of the day of entry into the study including study number, patient identification number, verification that the trial was discussed and written informed consent was obtained
 - iv. Dated notes for each protocol assessment and documentation that protocol specific procedures were performed
 - v. Study drug accountability (investigator must keep blinded records of volume of study drug given and timing of each daily dose based on the hospital chart; this will not entail review of the unblinded pharmacy records for the sake of maintaining the blind)
 - vi. Documentation of all adverse events, including any action taken with regard to study drug and outcome
 - vii. Concomitant medications (including start and end date, dose if relevant)
 - viii. Date of trial completion and reason for early discontinuation, if applicable

10. Confidentiality

- a. The investigator must ensure that all participants' confidentiality will be strictly maintained and that their identities are protected from unauthorized parties. Only patient initials, date of birth, and an identification code (i.e., not names) should be recorded on any form or biological sample submitted to the sponsor, IRB, or laboratory. The investigator must keep a screening log showing codes, names and addresses for all patients screened and for all patients enrolled in the trial. On CRFs or other documents that are submitted to the sponsor, participants should be identified by an identification code and not by their names.
- b. The investigator agrees that all information received from the Sponsor, including but not limited to the Investigator Brochure, the investigational product, and any other study information, remain the sole and exclusive property of the Sponsor during the conduct of the study and thereafter. This information is not to be disclosed to any third party (except employees or agents directly involved in the conduct of the study or as required by law) without prior written consent from the Sponsor. The investigator further agrees to take all reasonable precautions to prevent the disclosure by any employee or agent of the study site to any third party or otherwise into the public domain.

11. Publication

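### The per-protocol set is defined by days of hospitalization in a trial with no planned inpatient stay, so its dosing and laxative criteria are wrong as written; the consequence is limited

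*Combined protocol and SAP*

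**What the plan says.** Section VI.4.a.iii defines the PP set as "All patients who are randomized and receive the study medication on each day of their hospitalization". Under major protocol violations it lists one item: "Prohibited concomitant medication usage (specifically standing laxatives during hospitalization". On use, it says: "The PP population may be used for supplementary analysis of selected efficacy and safety data, as appropriate". The same section makes the ITT population, all randomized patients, primary for efficacy.

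Section V.a.3 describes the treatment period. Item c: "During 3-week treatment period, patients will ingest three capsules, twice daily, before breakfast and dinner". Item g (Day 15): "Following 14 days of treatment, patients will return to the clinic to undergo WMC testing to establish their motility profile on treatment". Item h (Day 22): "Following 21 days of treatment, patients will return to the clinic to return the WMC monitor". Treatment also starts from a clinic visit on Day 0 (item a). The diary in item e is one "which includes daily recording of number and time of bowel movements, complete/incomplete evacuation, and straining, abdominal discomfort, bloating, constipation severity, and overall relief"; capsule intake is not among the items listed.

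For drug accountability, Section IX.9.b.v requires "blinded records of volume of study drug given and timing of each daily dose based on the hospital chart". Section IX.9.a also asks for receipt and dispensing records.

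On laxatives, Section V.a.6 bars standing use for prophylaxis in enrolled patients and permits as-needed rescue.

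**The concern.** Both PP criteria are anchored to a period that the design does not contain. Patients come from a clinic and from online advertisements and return to clinic for their visits. Admission to hospital otherwise appears only as a criterion for a serious adverse event. That capsules are taken at home is an inference from the visit schedule, but no other setting is described.

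The PP set is the only supplementary efficacy population named. Its use would be to show whether the colonic transit time (CTT) result holds in patients who took the product as planned. If two analysts can build very different sets from the same data, and the choice is made after unblinding, it cannot serve that purpose.

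**Working it through.** **1. Literal reading.** A patient with no hospital day meets an every-day-of-hospitalization rule trivially, so the set is everyone randomized. If an actual stay is required, only patients with an unplanned admission could qualify, which is close to none. On either version the laxative criterion covers no planned treatment day.

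**2. Charitable reading: hospitalization means treatment period.** Two questions stay open.

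- *Which days.* Section V.a.3 is headed Day 0 to 22, which spans 23 calendar days. First dosing is on Day 1, and Day 22 follows 21 days of treatment, which gives Days 1 to 21.
- *What counts as a day on medication.* The schedule is 3 × 2 = 6 capsules a day: 14 × 6 = 84 before the Day 15 motility capsule test, 7 × 6 = 42 over Days 15 to 21, and 126 in all. The PP text does not say whether one of the two doses suffices. If it does, a patient taking one dose every day (63 of 126, 50%) is kept, while a patient missing one whole day (120 of 126, 95%) is removed.

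**3. Size of the partial-dose ambiguity (illustration).** The documents give no adherence rate. Let q be per-dose adherence, independent across doses, over 21 days:

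- any dose each day: (1 − (1 − q)²)^21
- both doses each day: q^42

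| Assumed q | Any dose: kept of 45 | Both doses: kept of 45 |
|---|---|---|
| 0.99 | 44.9 | 29.5 |
| 0.98 | 44.6 | 19.3 |
| 0.95 | 0.9975^21 = 0.949, so 42.7 | 0.95^42 = 0.116, so 5.2 |

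**4. Does any stated figure depend on this?** No. The power in Section VI.4.c reproduces without reference to the PP set. Inputs are mean reductions of 0, 10 and 13 h (or 11 h), SD 12 h at one time point, correlation 0.7, and two-sided alpha 0.05 (assumed, as none is stated).

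- SD of change = 12 × √(2 × (1 − 0.7)) = 9.30 h.
- Noncentrality = N × (mean squared deviation of the group means) / 9.30², with 2 and N − 3 degrees of freedom.

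| Case | Stated | 12 h as SD at one time point | 12 h as SD of change |
|---|---|---|---|
| 3 h extra, N = 45 | 94% | 94.3% | 77% |
| 3 h extra, N = 30 | 80% | 79.8% | 57% |
| 1 h extra, N = 45 | 88% | 88.2% | 67% |

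The plan's own figures therefore show that 12 h is the SD at one time point.

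**5. Precision of a smaller set.** The 95% CI half-width for a pairwise difference in CTT change is t(0.975, 3n − 3) × 9.30 × √(2/n).

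- n = 15 per arm: 2.018 × 9.30 × 0.365 = 6.8 h
- n = 10 per arm (assumed): 2.052 × 9.30 × 0.447 = 8.5 h

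**The case against.** The best defence is that this is carried-over wording in an optional analysis of an exploratory pilot, and that any reader would substitute treatment period. The limit on consequence stands. The substitution does not finish the repair, because it leaves the day range and partial dosing undefined.

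Four stronger readings are tempting, and the documents do not support them.

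- *The laxative rules are contradictory throughout, so no violation can be identified.* Section V.a.6 already separates barred standing use from permitted as-needed rescue, and the unrestricted access in Section V.b.2.a concerns as-needed doses. Exclusion criterion 4 and the stable-dose exception in Section V.a.2 govern the run-in, before randomization. What the PP criterion lacks is a valid window.
- *There is no record of dosing at all.* Sections IX.9.a and IX.9.b.v do require accountability records, and the diary list may not be exhaustive. The fair criticism is that the named source, a hospital chart, does not fit outpatient dosing.
- *Most patients would be lost.* The retention figures rest on assumed, independent adherence. If missed doses cluster in a few patients, more would survive the strict rule and the gap would narrow. The any-dose figures also need one dose to count as receiving the medication, although the schedule is twice daily.
- *The listed violation is the only one possible.* The violations list is introduced in open-ended terms.

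**Conclusion.** The PP definition is wrong as written, not merely short of detail. Both criteria refer to a hospital stay that the design does not include. Followed literally, the dosing rule keeps everyone or almost no one. Read charitably, it could keep about 43 or about 5 of 45 patients at an assumed 95% independent per-dose adherence, depending on a choice the plan does not make. That range illustrates the ambiguity and is not a forecast.

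A reader might infer that the primary result or the sample size is compromised. Neither is: ITT is primary for efficacy, the PP set is optional, and the stated 94%, 80% and 88% power reproduce without it. The correction should be made because it is cheap and because the PP set has no dependable meaning without it.

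**What to change.** 1. Replace hospitalization in both PP criteria with stated outpatient study days.
2. Define adherence as a share of scheduled capsules, fixed before unblinding, from Day 1 until the on-treatment motility capsule exits, or to Day 22 if exit is not recorded. A fixed window to Day 22 would be too blunt. A patient whose capsule exits by the end of Day 17 and who then stops has taken 84 of 84 and 18 of 42 (43%), and could fail although CTT was measured wholly on treatment.
3. Take adherence from returned capsules counted at the existing Day 15 and Day 22 visits, and correct the source named in Section IX.9.b.v. A count does not date doses within Days 15 to 21, so state how intake up to exit is derived, for example from a capsule-intake line in the existing diary.
4. Count as the violation standing laxative use from Day 1 to the end of the on-treatment motility test, using the distinction from as-needed rescue already in Section V.a.6.
5. Do not require a valid CTT for PP membership, since a capsule that has not passed is related to the outcome. Report missing CTT separately.
6. Reconcile exclusion criterion 4 with the stable-dose exception in Section V.a.2 as a separate eligibility point.

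The cost is revised wording, two capsule counts at visits already scheduled, and a smaller set. If 10 per arm remained (assumed), the CI half-width for a pairwise difference in CTT change would widen from about 6.8 h to about 8.5 h.
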